9.2.7.1 Secondary Efficacy Sensitivity Analyses

The secondary analysis described for each of the secondary endpoints listed above will be repeated using the per-protocol population as a sensitivity analysis.

9.2.8 Exploratory Subgroup Analyses (Secondary Endpoints)

Exploratory subgroup analyses for the subgroup categories outlined in [Section 9.1.4](#) will be performed for the time to death through 1 year after randomization secondary efficacy outcome described in [Section 9.2.1](#). The subgroup analyses will be performed for both the ITT population and the per-protocol population. Because hypothesis testing is not performed and p-values are not reported for subgroup analyses, the fixed-sequence testing methodology does not apply to subgroup analyses.

9.3 Exploratory Endpoints

The analysis of the exploratory endpoints will be performed for the ITT population. Exploratory endpoint scores and sub scores will be derived using clinical parameter results reported in the central laboratory dataset. For the clinical parameters not included as part of the central laboratory tests, results will be taken from the relevant eCRF pages.

9.3.1 Incidence of ACLF at 3, 6 and 12 Months

ACLF is evaluated monthly through Month 12 and will be listed.

The number and percentage of subjects with at least one occurrence of ACLF from Month 1 through Month 3 will be presented by treatment, and treatment differences will be analyzed by the Chi-square test. Month 1 is inclusive of the occurrences reported at the Day 11 and Month 1 scheduled visits.

The same summary and analysis will be performed for the ACLF evaluations occurring from Month 1 through Month 3, from Month 1 through Month 6, and for all ACLF evaluations occurring from Month 1 through Month 12.

GRIFOLS	Number	BIG-CL-SP-000319	Version	2.0	Status	Effective	Effective Date	09-Sep-2024	Page	34 of 52
	IG1601	Statistical Analysis Plan								

In addition, the ACLF evaluations will be summarized by treatment group for each visit, reporting number and percentage of subjects reporting ACLF and the ACLF grade by visit.

9.3.2 CLIF-C OF Score and Sub Scores for Organ Function

CLIF-C OF score is evaluated monthly through Month 12 and will be listed.

The CLIF-C OF score system consists of six sub-scores for liver, kidney, brain, coagulation, circulatory, and respiratory organs/systems – each with values of 1, 2 or 3 with a higher number representing more severe disease. Each CLIF-C OF sub-score will be summarized as a categorical variable by treatment for each visit.

The total CLIF-C OF score is a discrete numeric value in the range of 6 to 18 (inclusive) and is defined as the sum of the six organ/system sub-scores. If an individual sub-score is missing, the total score will also be missing. The total CLIF-C OF score and change in total score from baseline to each scheduled post-baseline visit will be summarized, as a continuous variable, by treatment and scheduled visit. In addition, the total score change from baseline of scheduled visits for both treatment groups will be analyzed by MMRM, which includes change in total score from baseline as the dependent variable; treatment, visit, region (Europe or North America) and history of hospitalization for acute decompensation of liver cirrhosis (yes or no), treatment-by-visit interaction, region-by-visit interaction, and history of hospitalization for acute decompensation of liver cirrhosis-by-visit interaction as fixed effects; baseline and baseline-by-visit as covariates; and measures within-subject at each visit as a repeated measure. The model employs an unstructured covariance matrix for the within-subject dependence. If the model fails to converge, the mixed effects model with a compound symmetry correlation structure will be used.

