3.1.3 Exploratory Efficacy Objectives

The effects of SMT + Albutein 20% administration versus SMT alone on the following parameters will be evaluated:

- 3-, 6-, and 12-month incidence of ACLF according to the EASL-CLIF Consortium (CLIF-C) definition (24)
- Incidence of individual organ failures: liver, renal, cerebral, coagulation, respiration, and circulation as defined by the CLIF-C Organ Failure (CLIF-C OF) score and the total CLIF-C OF score (Appendix 3)
- · Readmissions to the hospital due to an acute complication of cirrhosis
- Admissions to intensive care units (ICU)
- Incidence of disease-related complications (see Section 8.3.10)
- Serum albumin concentration and albumin functional capacity in serum (albumin binding capacity [Table 7-1])
- Incidence of transjugular intrahepatic portosystemic shunt (TIPS) insertion for refractory ascites
- CLIF-C Acute-on-chronic liver failure (CLIF-C ACLF) score, CLIF-C Acute Decompensation (CLIF-C AD) score, Model for End-stage Liver Disease (MELD) score, and Child Pugh score
- Subject's quality of life according to the EuroQol 5 Dimensions 5 Levels (EQ-5D-5L) health questionnaire (Appendix 5).

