7.1.3 Exploratory Variables

- Incidence of ACLF (3, 6, and 12 months)
- Organ function subscores (liver, renal, cerebral, coagulation, circulation, and respiration), according to the CLIF-C OF score and the total CLIF-C OF score (Appendix 3)
- Number and length of hospital readmission for an acute complication of cirrhosis
- Number and length of ICU admission
- Incidence of disease-related complications (see Section 8.3.10)
- Serum albumin concentration and albumin functional capacity in serum (albumin binding capacity [Table 7-1])
- Incidence of insertion of TIPS for refractory ascites
- CLIF-C ACLF score ,CLIF-C AD score, MELD score, and Child Pugh score
- Quality of life: EQ-5D-5L health questionnaire (Appendix 5)

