9.1.2.3 Exploratory Endpoints

As appropriate to the data, the original values or changes from baseline (last measurement taken prior to the start of study treatment on Day 1) of the following exploratory endpoints will be listed for each subject, summarized by treatment group, and compared between treatment groups by means of ANCOVA or Student's t tests (for normally-distributed variables), non-parametric Mann-Whitney U test (for non-parametric variables), Kaplan-Meier estimates and Log-rank test (for time-to-event variables), Poisson regression model (for count variables), and Fisher's exact test or Chi-square test (for binomial variables):

Incidence of ACLF, CLIF-C OF score, CLIF-C ACLF score, CLIF-C AD score, MELD score, Child Pugh score, number and length of hospital readmission for an acute complication of cirrhosis, number and length of ICU admission, incidence of disease-related complications, serum albumin concentration, albumin functional capacity (albumin binding capacity), incidence of insertion of TIPS for refractory ascites, and the EQ-5D-5L health questionnaire.

For the normally-distributed variables, the ANCOVA model will include change from baseline as the dependent variable, treatment as a fixed factor, and baseline value as a covariate. If any potential confounders are identified among subjects' baseline characteristics, they will be included as additional covariates in the ANCOVA models to adjust treatment effects. In addition, for the longitudinal measurements taken repeatedly over time, the treatment effects may be explored by using the mixed-effect model repeated measures analysis.

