4.1.3 Exploratory Efficacy Objectives

The effects of SMT + Albutein 20% administration versus SMT alone on the following parameters will be evaluated:

- 3-, 6-, and 12-month incidence of ACLF according to the European Association for the Study of Liver -Chronic Liver Failure (EASL-CLIF) Consortium definition (11)
- Incidence of individual organ failures: liver, renal, cerebral, coagulation, respiration, and circulation as defined by the CLIF-Consortium Organ Failure (CLIF-C OF) score

Number	IG1601	IG1601 Statistical Analysis Plan
Version	2.0	
Status		
Effective		

Number	IG1601	IG1601 Statistical Analysis Plan
Version	2.0	
Status		
Effective		

Effective Date	09-Sep-2024
Page	13 of 52

- Readmissions to the hospital due to an acute complication of cirrhosis
- Admissions to intensive care units (ICU)
- Incidence of disease-related complications (anticipated disease progression includes, but not limited to HE, gastrointestinal [GI] bleeding, portal hypertension, ascites, SBP, hyponatremia and HRS)
- Serum albumin concentration and albumin functional capacity in serum (albumin binding capacity)
- Incidence of transjugular intrahepatic portosystemic shunt (TIPS) insertion for refractory ascites
- CLIF-C Acute-on-chronic liver failure (CLIF-C ACLF) score, CLIF-C Acute Decompensation (CLIF-C AD) score, Model for End-Stage Liver Disease (MELD) score, and Child-Pugh score
- Subject's quality of life according to the EuroQol 5 Dimensions 5 Levels (EQ-5D-5L) health questionnaire

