6.1.5 Visit Windows

For safety analyses (laboratory and vital signs data) and efficacy analyses, by-visit summaries and analyses will analyze assessments by visit as designated on the CRF; visit remapping based on study day to an analysis visit window won't be applied. Unscheduled visits will be excluded from by-visit summaries and analyses. The Early Discontinuation

GRIFOLS	Bioscience Industrial Group	Number	IG1601	Version	2.0	Status	Effective	Effective Date	09-Sep-2024	Page	20 of 52
		IG1601	Statistical Analysis Plan								

visit will be summarized as a separate visit, without adjusting for the timing of assessments for subjects that discontinue early.

For the analyses of exploratory endpoints, the early discontinuation visit will be mapped to an assessment visit. The mapping will be based on the timing of a subject's assessment visit, relative to their Study Day 1. A detailed list of the parameters and the mapping rules to be applied is provided in [Appendix 4](#).

For cases where multiple assessments are recorded for a parameter within a single visit window, the following rules will be applied for each parameter:

- If 2 or more assessments are mapped to the same visit window, then the non-missing assessment closest to the scheduled visit target day will be used in the analysis.
- If 2 assessments are equidistant from the visit target day, the later non-missing observation will be used in the analysis.

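### Incidence of individual organ failures is an exploratory objective in both documents, but SAP 9.3.2 only tabulates sub-scores visit by visit, with no incidence, failure cut-off or between-arm comparison for any organ

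*SAP*

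**What the plan says.** The objective is worded as an incidence in both documents. Protocol 3.1.3 has "Incidence of individual organ failures: liver, renal, cerebral, coagulation, respiration, and circulation as defined by the CLIF-C Organ Failure (CLIF-C OF) score", with the total score in the same bullet. SAP 4.1.3 has "Incidence of individual organ failures: liver, renal, cerebral, coagulation, respiration, and circulation as defined by the CLIF-Consortium Organ Failure (CLIF-C OF) score". Both stand under an opening line that promises a comparison with SMT alone.

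The variable lists then change the wording. Protocol 7.1.3 has "Organ function subscores (liver, renal, cerebral, coagulation, circulation, and respiration), according to the CLIF-C OF score and the total CLIF-C OF score", and SAP 5.4.1 likewise lists sub-scores, so incidence drops out at this step. Protocol 9.1.2.3 still puts the score among the endpoints to be compared between groups: "Incidence of ACLF, CLIF-C OF score, CLIF-C ACLF score, CLIF-C AD score, MELD score, Child Pugh score".

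SAP 9.3.2 gives the separate organs one analysis: "Each CLIF-C OF sub-score will be summarized as a categorical variable by treatment for each visit". The only comparison in that section concerns the total: "the total score change from baseline of scheduled visits for both treatment groups will be analyzed by MMRM".

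Two general rules apply. SAP 6.1.1 leaves missing visit values missing, and SAP 6.1.5 adds "Unscheduled visits will be excluded from by-visit summaries and analyses".

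**The concern.** An objective about how many subjects develop liver, renal, cerebral, coagulation, respiratory or circulatory failure needs, for each organ, a definition of failure, a count of subjects who reach it over a stated period, and a contrast between arms. SAP 9.3.2 has none of the three. A table of sub-scores 1, 2 and 3 at Month 4 says who was in that state on that day among those assessed. It does not say who has ever been in it. Followed as written, the plan leaves a stated objective unanswered in the study report, although scheduled sub-scores are available from Day 11 to Month 12. Any organ-specific incidence would then have to be devised after the data have been seen, including the choice of cut-off.

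**Working it through.** **1. Is the analysis elsewhere in the SAP?** The neighbouring sections, set side by side:

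- 9.3.1, ACLF: subjects with one or more occurrences, cumulated to Months 3, 6 and 12, with a chi-square test. Not organ-specific.
- 9.3.2, total CLIF-C OF score: mixed model for change from baseline. Sums over organs.
- 9.3.2, separate sub-scores: by-visit frequencies only.
- 9.3.5, Child-Pugh sub-scores: compared by a proportional-odds model.
- 9.3.8, complications: HE and HRS are compared by logistic model. These touch two of the six organs and use other definitions.
- 12, changes from the protocol: no mention of dropping organ-failure incidence.

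So the gap is specific to organ failures, and no other section fills it.

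**2. Is failure defined?** SAP 9.3.2 gives no cut-off. Protocol Appendix 3 marks failure by shaded cells, organ by organ. A uniform sub-score of 3 would probably be wrong for the kidney. Appendix 3 places creatinine from 2 to below 3.5 mg/dL in sub-score 2. Table 2-1 separates single kidney failure (grade 1a) from another single failure with creatinine 1.5 to 1.9 mg/dL (grade 1b), which implies that renal failure starts at about 2 mg/dL.

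**3. Who is at risk?** In Table 2-1 the no-ACLF row admits one failure of liver, coagulation, circulation or respiration. Subjects without ACLF at Screening can therefore already have an organ failure, and an incidence has to exclude them for that organ.

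**4. How far is by-visit prevalence from incidence?** The documents give no organ-failure rate, so what follows is illustration on stated assumptions.

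Inputs from SAP 6.2: one-year transplant or death 46% versus 31%, 205 per arm. Check of the plan's own figure: ln(0.69)/ln(0.54) = 0.6022, as stated.

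Subjects still event-free at Day 361, exponential, before dropout:

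- SMT: 205 × 0.54^(361/365) = 111
- Albutein: 205 × 0.69^(361/365) = 142

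This treats every event as a death. Under Protocol 5.3.2, transplanted subjects continue planned visits, so the true loss from the tables is smaller.

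Now assume visits 30 days apart, onset uniform within the interval, and exponential episode length with mean m days, the same in both arms. The share of episodes still present at the next visit is (m/30)(1 − e^(−30/m)):

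- m = 5: 0.167 × 0.998 = 0.166
- m = 10: 0.333 × 0.950 = 0.317
- m = 20: 0.667 × 0.777 = 0.518

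Borrow 46% and 31% as the one-year incidence of a failure (again an assumption). The percentages ever seen in failure at a scheduled visit are then:

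- m = 5: 7.6% versus 5.2%
- m = 10: 14.6% versus 9.8%
- m = 20: 23.8% versus 16.1%

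At any one visit the prevalence is at most about onset rate × m. For m = 10:

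- SMT: (0.616/365) × 10 = 1.7%
- Albutein: (0.371/365) × 10 = 1.0%

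The between-arm ratio stays near 46/31 = 1.48 throughout. What is lost is information, not direction.

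**The case against.** The best defence has five parts.

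- The endpoint is exploratory, and SAP 9.3.2 does follow the protocol's variable list, which names sub-scores. True, but the objective that the variable serves is still worded as incidence in both documents.
- Related results are planned: the total score, ACLF incidence, HE and HRS. This is partial cover. None reports liver, coagulation, circulatory or respiratory failure.
- SAP 9.3.2 lists CLIF-C OF scores, and SAP 2 allows unplanned analyses if they are documented. That permits a later analysis but does not prespecify one.
- Early-discontinuation visits are already mapped to windows for the sub-scores (SAP 6.1.5 and Appendix 4). This stands, and the fix should use those visits.
- The harder limit is data collection. The score is scheduled only at Screening, Day 11, monthly and at Month 12 or early discontinuation, and nothing requires it at readmission or death. This also stands. A failure that begins between visits and ends in death will mostly go unscored, and no SAP wording recovers it.

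A reader might go further and infer that the tables rest on survivors only, so that the arm with more fatal organ failure could look as good as the other or better. The documents do not support that. SAP 9.3 names the ITT population, and no per-visit percentage denominator is stated. An ITT denominator would not give an incidence either, because it would count the dead as not in failure. No fatality rate for single organ failures is given, and a very high one would sit badly with Protocol Table 2-2, where 28-day mortality is 22.1% in ACLF grade 1 and 32.0% in grade 2, reaching 76.7% only in grade 3. The illustration above keeps the direction of effect.

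**Conclusion.** The mismatch is real and can be read directly from the text: for none of the six organs does the SAP plan an incidence, a failure cut-off or a comparison, and no other section supplies one. By-visit prevalence without imputation and without unscheduled visits is a different quantity from incidence. On the assumed 5- to 20-day episodes, scheduled visits catch 17% to 52% of failures, and a single visit table shows only a percent or two at m = 10. Those sizes are assumption only, including equal episode length in both arms. If episodes were shorter in one arm the ratio would shift, but the documents give nothing with which to size that.

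The consequence is limited to an unanswered exploratory objective. The primary analysis and the alpha-controlled secondary sequence are not affected. This is a worthwhile improvement, not a threat to the trial's conclusions.

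**What to change.** In SAP 9.3.2:

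- Define failure for each organ by the organ-specific criteria in protocol Appendix 3, written out in the SAP, and not as a uniform sub-score of 3.
- Among ITT subjects without that failure at baseline, report by arm the number and percentage with one or more failures through Months 3, 6 and 12, on the pattern of SAP 9.3.1.
- Use every recorded assessment: scheduled, mapped early-discontinuation and any unscheduled. Say explicitly that the exclusion in SAP 6.1.5 does not apply to this count.
- Give a between-arm estimate with 95% CI. Preferably present cumulative incidence with death and transplant as competing events; the simple count as for ACLF would already meet the objective.
- State the denominator of the by-visit tables and keep them as description.
- Note that failures between visits without a recorded score are not captured, so the reported incidence is a lower bound.

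The cost is SAP wording and a few exploratory tables from data already scheduled for collection. The downside is six more unadjusted exploratory comparisons, which should be labelled as such.

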5.2.3 Treatment Day 11 and Monthly Visits (Month 1 through Month 11)

Subjects will have assessments on Day 11 (± 2 days), Month 1 (± 2 days), and then monthly (± 2 days) for up to 11 months: Days, 61, 91, 121, 151, 181, 211, 241, 271, 301, 331 (See [Section 5.2.5](#) for Day 361 assessments). All assessments and activities will be performed prior to Albutein treatment for the SMT + Albutein 20% treatment group. In addition, for the SMT + Albutein 20% treatment group, vital signs and serum albumin concentration will also be recorded after treatment.

5.2.4 SMT + Albutein 20% Treatment Days 21, 41, 51, 71, 81, 101, 111, 131, 141, 161, 171, 191, 201, 221, 231, 251, 261, 281, 291, 311, 321, 341, and 351

Subjects in the SMT + Albutein 20% treatment group will receive Albutein infusions every 10 (± 2) days for up to 12 months in the study. All assessments and activities will be performed prior to Albutein infusion, and in addition vital signs will also be recorded after Albutein infusion. These treatment day visits apply to the SMT + Albutein 20% treatment group only; subjects in the SMT treatment group will not have assessments on these study days.

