5.2.5 Month 12 / Early Discontinuation

All subjects will have assessments at Month 12 (Day 361 ± 2 days)/Early Discontinuation. Subjects in the SMT + Albutein 20% treatment group will receive an Albutein infusion at Month 12. All assessments and activities will be performed prior to treatment for SMT + Albutein 20% treatment group. In the SMT + Albutein 20% treatment group, vital signs and serum albumin concentration will also be recorded after Albutein infusion.

Subjects who discontinue from the study early will complete the assessments that are planned for the Month 12 visit.

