9.3.4 MELD Score

The Model for End-stage Liver Disease (MELD) score is a continuous numeric value in the range of 6-40, with a higher number representing more severe disease, and is defined as:

$$\text{MELD} = 9.57 * \text{Ln}(\text{Creatinine } \{ \text{mg/dl} \}) + 3.78 * \text{Ln}(\text{Bilirubin } \{ \text{mg/dl} \}) + 11.2 * \text{Ln}(\text{INR}) + 6.43.$$

MELD scores are evaluated monthly through Month 12 and will be listed. If any of the individual clinical parameters used to derive the MELD score report results <1, the result is imputed to 1, and then used to generate the MELD score.

The MELD score will be summarized as a continuous variable. The MELD total score and change in total score from baseline to each scheduled post-baseline visit will be summarized, as a continuous variable, by treatment and scheduled visit. In addition, the MMRM analysis of CLIF-C OF scores will be repeated for the change from baseline total scores

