9.3.5 Child-Pugh Score

The Child-Turcotte-Pugh (Child-Pugh) classification for severity of cirrhosis consists of 5 sub-scores for encephalopathy, ascites, bilirubin, albumin, and INR – each with values of 1, 2 or 3 with a higher number representing more severe disease. Refer to protocol Appendix 3 for details. The Child-Pugh Score is a discrete numeric value in the range of 5 to 15 (inclusive) and is defined as the sum of the five sub-scores. If an individual sub-score is missing, the total score will also be missing.

The Child-Pugh Class is derived from the Child-Pugh Score as follows: Class A = score of 5-6; Class B = score of 7-9; Class C = score of 10-15.

Child-Pugh scores are evaluated monthly through Month 12 and will be listed.

Each Child-Pugh sub-score will be summarized as a categorical variable by treatment and scheduled visit. In addition, each Child-Pugh sub-score will be compared by treatment and scheduled visit using the generalized linear models implemented in SAS GENMOD procedure, in which each Child-Pugh sub-score is modeled by the proportional odds

Number	IG1601 Statistical Analysis Plan		
	Version	2.0	Status
Effective	Effective Date	09-Sep-2024	Page
36 of 52			

cumulative logit model for multinomial data with adjustment for, baseline score, region (Europe or North America), history of hospitalization for acute decompensation of liver cirrhosis (yes or no), treatment, visit and treatment-by-visit interaction as independent variables, and the robust variance estimate for the treatment effect will be estimated based on the independent working correlation structure.

The Child-Pugh Total Score and change in total score from baseline to each scheduled post-baseline visit will be summarized, as a continuous variable, by treatment group and scheduled visit. In addition, the MMRM analysis of CLIF-C OF scores will be repeated for the change from baseline total scores.

The Child-Pugh Class will be summarized as a categorical variable by treatment for each visit.

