9.3.11 Quality of Life: EQ-5D-5L Health Questionnaire

The EuroQoL 5 Dimensions 5 Levels (EQ-5D-5L) questionnaire is assessed monthly through Month 12; all data will be listed.

The EQ-5D-5L health questionnaire consists of five-dimension scores for mobility, self-care, usual activities, pain/discomfort, and anxiety/depression. Each dimension score has values of 1-5 with a higher number representing worse quality of life. Refer to protocol Appendix 5 for more details. Each EQ-5D-5L domain score will be summarized as a categorical variable by treatment for each visit.

The EQ-5D-5L health profile, defined by the EQ-5D-5L descriptive system, may be converted into a single index score on the basis of the US set of weights using the EuroQol value level dataset which contains the values of the EQ-5D-5L crosswalk index values (19). The US EQ-5D-5L index score is a numeric value in the range of -0.109 to 1.00 with a higher number generally representing a better quality of life. The EQ-5D-5L index score will be summarized as a continuous variable. The index score and change from baseline will be summarized by treatment for each visit. In addition, the change from baseline will be compared at visits with data collected for both treatment groups using the same method as that for CLIF-C OF scores.

GRIFOLS	Bioscience Industrial Group	Number	IG1601	Statistical Analysis Plan
		Version	2.0	Page
09-Sep-2024	40 of 52	Effective Date	Effective	

The EQ-5D-5L Visual Analog Scale (EQ VAS) rates the subject's health on a scale of 0 to 100, with a higher number representing better health. The EQ VAS score will be summarized as a continuous variable. The VAS score and change from baseline will be summarized by treatment for each scheduled visit. In addition, the change from baseline will be compared for scheduled visits with data collected for both treatment groups in the same way as CLIF-C OF scores.

10 Safety Analysis

Unless otherwise noted, all Safety listings and summaries will be based on the Safety population.

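### The only fallback for the unstructured MMRM is compound symmetry with no robust variance named, so exploratory score comparisons could carry the wrong precision visit by visit

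*SAP*

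**What the plan says.** SAP 9.3.2 fits change from baseline in CLIF-C OF total score with treatment, visit, region and hospitalization history, the interaction of visit with each of the other three, and "baseline and baseline-by-visit as covariates". On covariance it says "The model employs an unstructured covariance matrix for the within-subject dependence", followed by the single fallback "If the model fails to converge, the mixed effects model with a compound symmetry correlation structure will be used". For this model it names neither a type of standard error nor a degrees-of-freedom method.

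Other endpoints inherit the model by reference. SAP 9.3.4 (MELD) says "the MMRM analysis of CLIF-C OF scores will be repeated for the change from baseline total scores", and 9.3.11 compares EQ-5D-5L change "using the same method as that for CLIF-C OF scores". Sections 9.3.3, 9.3.5 (Child-Pugh total) and 9.3.9 (serum albumin and albumin binding capacity) do the same.

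The SAP is more explicit for its GENMOD models. In 9.3.5, "the robust variance estimate for the treatment effect will be estimated based on the independent working correlation structure". In 9.3.8 a robust variance comes with three working correlations to be tried in order.

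The visit count comes from 5.2.3 ("Subjects will have assessments on Day 11 (± 2 days), Month 1 (± 2 days), and then monthly", through Month 11) and 5.2.5 ("All subjects will have assessments at Month 12 (Day 361 ± 2 days)/Early Discontinuation").

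**The concern.** Homogeneous compound symmetry assumes the same variance at Day 11 as at Month 12, and the same correlation between those two visits as between adjacent months. Change adjusted for baseline is unlikely to behave that way. Soon after baseline the residual variance tends to be small; later it tends to be larger, and correlation usually weakens as visits move apart.

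Two features make the structure matter. SAP 6.1.1 imputes nothing for longitudinal outcomes, so the modelled covariance carries the information from subjects who leave. The first-choice model is also large. The revision history (items 23 and 26) says that baseline and stratification interactions with time were dropped from GENMOD models as over-specified, while the MMRM keeps its own.

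At stake is the precision of exploratory treatment differences. Late intervals could be too narrow and early ones too wide. SAP section 2 intends the planned analyses for the study report and for submissions or manuscripts, and no multiplicity control applies to these endpoints.

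**Working it through.** **1. Inputs from the documents.** 205 subjects per arm; 1-year event rates of 46% and 31%; dropout 20%; two-sided alpha 0.05 (SAP 6.2 and 6.5). These rates reproduce the plan's own figures: HR = ln(0.69)/ln(0.54) = 0.6022, and 205 x 0.8 = 164 per arm gives 80.0% power for the chi-square test. The documents give no SD, within-subject correlation or standard error for the MMRM, so everything from step 4 on rests on assumed covariances.

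**2. Size of the unstructured model.** Day 11, Months 1-11 and Month 12 make 1 + 11 + 1 = 13 post-baseline visits, hence 13 x 14/2 = 91 covariance parameters. This holds for CLIF-C OF, CLIF-C ACLF, CLIF-C AD, MELD, Child-Pugh total and serum albumin. By the schedule (SAP Appendix 1), EQ-5D-5L has 5 post-baseline visits (5 x 6/2 = 15 parameters) and albumin binding capacity has 6 (6 x 7/2 = 21).

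**3. Retention.** Average event-free proportion (0.54 + 0.69)/2 = 0.615; times 0.8 for dropout = 0.49. Transplanted subjects keep their planned visits (Protocol 5.3.2), so events are not all losses to these analyses. A range of 40-80% at Month 12 was used.

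**4. Method.** Let V_k be the compound-symmetry matrix, and S_k the true matrix, for subjects last seen at visit k, a fraction p_k. The compound-symmetry parameters are set to their likelihood limits.

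- A = sum of p_k V_k^-1 and B = sum of p_k V_k^-1 S_k V_k^-1, each padded with zeros.
- Model-based variance is proportional to A^-1; true (sandwich) variance to A^-1 B A^-1.
- q = model-based SE / true SE at the visit; type I error = 2[1 - Phi(1.96 q)].

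Assumed: normal outcomes, monotone completely random dropout, equal arms, and region and hospitalization-history terms omitted. Variances are in units of the cross-sectional score variance.

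**5. Example of the mechanism.** With AR(1) 0.9 per month conditional on baseline, the variance is 1 - 0.9^(2/3) = 0.07 at Day 11 and 1 - 0.9^24 = 0.92 at Month 12. At 40% retention compound symmetry fits one variance, 0.517. The Day 11 ratio is then about sqrt(0.517/0.068) = 2.76 (SE too large). The Month 12 ratio is 0.699 (SE too small), and 2[1 - Phi(1.96 x 0.699)] = 17.1%.

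**6. Month 12 results at about 50% retention, model-based SE.**

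| Assumed true covariance given baseline | SE understated by | Type I error |
|---|---|---|
| Compound symmetry | 0% | 5.0% |
| Random slope 0.03 / 0.05 / 0.08 / 0.12 SD per month | 6 / 15 / 26 / 36% | 6.7 / 9.4 / 14.5 / 20.6% |
| AR(1) 0.5 / 0.7 / 0.8 / 0.9 / 0.95 per month | 8 / 15 / 20 / 28 / 33% | 7.2 / 9.6 / 11.8 / 15.7 / 19.1% |
| AR(1) 0.8-0.95 with 20% measurement noise | 14-18% | 9.1-10.8% |
| AR(1), constant variance | 4-14% | 6.0-9.1% |

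Over 40-80% retention the full span is 0-37% understatement and 5.0-21.5% type I error. At Day 11 the ratio exceeds 1 in most scenarios conditioned on baseline, reaching about 3.4.

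**7. Effect of a sandwich SE.** Monte Carlo, 4,000 runs per case, 50% retention, same compound-symmetry fit:

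| True covariance | Model-based | Sandwich |
|---|---|---|
| AR(1) 0.9 | 15.5% | 5.7% |
| AR(1) 0.9 + 20% noise | 11.2% | 5.8% |
| Random slope 0.08 | 14.0% | 5.3% |
| Random slope 0.03 | 6.8% | 5.4% |
| Compound symmetry | 5.5% | 5.6% |

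**The case against.** **The trigger may never fire.** All these figures are conditional on the unstructured fit failing. In a simulation with 410 subjects, 13 visits, the SAP's model terms, 5% intermittent missingness and 46% or 57% loss (all assumed), maximum likelihood by EM converged in 160 of 160 datasets, with as few as 65 complete cases. That is not PROC MIXED with REML, so it does not rule failure out. It does show that visit count and attrition alone do not make failure likely. This stands.

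**The SAP does not say model-based.** A reader might infer that it commits to model-based standard errors. It is silent for this model, and the inference rests on what an analyst would run by default. This stands, and is part of the reason to specify it.

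**Compound symmetry correlation could mean the heterogeneous form.** The phrase also fits a structure with visit-specific variances. Under AR(1) 0.8-0.95 per month with 0-20% noise and 50-80% retention, plain compound symmetry gave 7.5-19% at Month 12 and the heterogeneous form 5-7%. Much of the inflation therefore depends on the equal-variance reading, and the text leaves it open.

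**Growing variance is not assured.** CLIF-C OF is bounded at 6-18 and the sickest subjects leave by death. This is fair, and it is why the range starts at 5%.

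**Only exploratory endpoints are involved, and Month 12 is not named as the key visit.** Both are correct, and both limit the importance.

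**Conclusion.** The point holds in a limited form. The SAP prescribes one step from the most flexible structure to a very restrictive one, without the robust variance that it uses for its other longitudinal models. If that step is taken with homogeneous compound symmetry and default standard errors, Month 12 type I error would be about 6-21% under the assumed covariances, and 5% if compound symmetry is true. Early standard errors would often be too large.

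A reader might infer a fixed size, such as a standard error too small by a quarter with 11-17% false positives. The documents do not support that. A 25% understatement does correspond to 14.2%, but it arises only under particular covariances, such as a random slope near 0.08 SD per month or AR(1) of about 0.8-0.9 per month given baseline. Nor do the documents show that the fallback is likely to be used, or that the argument applies equally to EQ-5D-5L (5 visits) and albumin binding capacity (6 visits), where failure is less likely.

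The primary test and the fixed sequence of secondary endpoints are unaffected. This is a change to consider.

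**What to change.** Replace the fallback sentence in SAP 9.3.2 with a prespecified order: unstructured, heterogeneous Toeplitz, heterogeneous AR(1), then compound symmetry, stopping at the first that converges. State that for any structure other than unstructured, tests and confidence intervals use the empirical (sandwich) variance (the EMPIRICAL option in PROC MIXED). The sections that refer back to 9.3.2 then inherit the rule.

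The cost is a few lines of SAP text and one SAS option. Late-visit intervals would be slightly wider than under default standard errors. The sandwich variance corrects the standard error, but it does not remove bias from a misspecified covariance when dropout depends on earlier scores. In simulations of the compound-symmetry fit that included such dropout, it gave 4-8% type I error, so the heterogeneous steps should come first.
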